## 8.2 Determination of Sample Size

The comparisons related to the primary and key secondary endpoints will be done in a hierarchical manner to control the familywise error rate. The testing procedure will start by testing the primary endpoint and then proceed to the key secondary endpoints by following the order as specified in Section 8.9.4.

A total of 170 subjects (85/arm) in 1:1 ratio to serlopitant 5 mg or placebo will provide 90% power to detect a 25% relative reduction (placebo-adjusted ratio of 0.75) in 24-hour objective cough frequency or awake objective cough frequency using a two-sample t-test at a one-sided significance level of 0.05. This assumes that 24-hour cough frequency or awake cough frequency follows a log-normal distribution with a CV of 0.64. This sample size also considers an expected dropout rate of 15%.

The sample size calculations have been performed in nQuery Advisor + nTerim.

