## 8.7 Multiplicity Adjustments

The study is designed to evaluate the efficacy profile of serlopitant 5 mg versus placebo. The sequential testing procedure will be employed to control the overall Type I error rate at 5% with respect to multiple comparisons for the primary and key secondary endpoints. The hypothesis testing procedure will be done in a hierarchical order as specified below:

- H1: Change from baseline in 24-hour objective cough frequency after 12 weeks (Day 84) of treatment.
- H2: Change from baseline in awake objective cough frequency after 12 weeks (Day 84) of treatment
- H3: Proportion of subjects with  $\geq 30\%$  reduction in 24-hour objective cough frequency per hour at Week 12 (Day 84)
- H4: Proportion of subjects with  $\geq 30\%$  reduction in awake objective cough frequency per hour at Week 12 (Day 84)
- H5: Change from Baseline in cough severity visual analog scale (VAS) at Week 12 (Day 84)

First, the test ranked as first will be tested and the difference will be declared statistically significant if the one-sided p value is less than 0.05. Second, in case that the difference for the first comparison is statistically significant, the comparison ranked as second will be tested, and the difference will be declared statistically significant if the one-sided p-value is less than 0.05. The testing will continue as long as the previously ranked objective was statistically significant.

All other efficacy variables will be tested at the 0.05 level of significance without multiplicity adjustment.

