### 9.6.1 Statistical Hypotheses and Tests

The study is designed to evaluate, the efficacy of serlopitant 5 mg relative to placebo. The primary hypothesis for this trial is that serlopitant is superior to placebo with respect to the mean change from baseline in 24-hour cough frequency (on the log scale).

Symbolically, the hypotheses for serlopitant 5 mg compared to placebo can be written as:

$$H_0: \mu_{SP, \text{Week 12}} - \mu_{SP, \text{Baseline}} = \mu_{PL, \text{Week 12}} - \mu_{PL, \text{Baseline}}$$

$$H_A: \mu_{SP, \text{Week 12}} - \mu_{SP, \text{Baseline}} < \mu_{PL, \text{Week 12}} - \mu_{PL, \text{Baseline}}$$

where  $\mu_{SP}$  and  $\mu_{PL}$  represent the mean values at Week 12 for serlopitant 5 mg and placebo, respectively.

As the primary endpoint, cough frequency, is to be analyzed on the log scale the null hypothesis relates to the ratio of Week 12/Baseline for serlopitant 5 mg being the same as that for placebo, and the alternative hypothesis being that the ratio of Week 12/Baseline for serlopitant 5 mg is smaller than the ratio for placebo.

A family wise error rate will be controlled to adjust for multiplicity for the comparison of serlopitant 5 mg to placebo on the primary and key efficacy endpoints in a hierarchical manner (see details in [Section 8.5](#)). One-sided p-values at 0.05 significance level will be used.

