An additional sensitivity analysis using the tipping-point approach will be conducted to assess the robustness of the primary analysis approach. If it is plausible that, for the active treatment group, the distribution of missing primary endpoint responses has a smaller expected reduction than that of the corresponding distribution of the observed primary endpoint responses, the conclusion under the MAR assumption should be examined. It is desired to impose a fixed and definite set of quantities to encapsulate the change in efficacy associated with withdrawal (missing) for the active treatment group, and the tipping point multiple imputation analysis as described in Ratitch et al. (2013) will be applied. Tipping point analysis is a means of exploring the influence of missingness on the overall conclusion from statistical inference by positing a wide spectrum of assumptions regarding the missingness mechanism (from less conservative to more conservative). The analysis finds a (tipping) point in this spectrum of assumptions, at which conclusions change from being favorable to the experimental treatment to being unfavorable. After such a tipping point is determined, clinical judgment can be applied as to the plausibility of the assumptions underlying this tipping point. The tipping point can be identified while the result is no longer statistically significant. This imputation analysis used a specified sequence of shift parameters, which adjust the imputed values for observations in the active treatment group. The tipping point can be identified while the result is no longer statistically significant. A sample of SAS code for sensitivity analysis using the tipping-point method is provided in Appendix A.

For both sensitivity analyses, the multiple imputations will be completed before log-transforming data.

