  SET _NULL_;
RUN;

/*----- # of shift values -----*/
%LET NCASE= %SYSEVALF( (&SMAX-&SMIN)/&SINC, CEIL );

/*---- Multiple imputation analysis for each shift ----*/
%DO JC=0 %TO &NCASE;
  %LET SJ= %SYSEVALF( &SMIN + &JC * &SINC);

  /*---- Generates 10 imputed data sets ----*/
```

```
/*Step 1: Achieve Monotone Missing Data Pattern */
PROC MI DATA=&DATA SEED=14823 NIMPUTE=10 OUT=MONO;
  ** Use numeric TRT01PN ;
  VAR BASE AVAL1 AVAL2 AVAL3; /*Refer to AVAL at Visits 5, 6, and 7*/
  MCMC IMPUTE=MONOTONE NBITER=5000 NITER =5000;
  BY TRT01PN;
run;

/*Step 2: Impute all visits under MAR first, then apply delta adjustments at
each visit*/
PROC MI DATA=OUTM1 SEED=14823 NIMPUTE=1 OUT=OUTM2;
  CLASS TRT01PN;
  BY _IMPUTATION_;
  VAR TRT01PN BASE AVAL1 AVAL2 AVAL3;
  MONOTONE REG (AVAL2 AVAL3);
  MNAR ADJUST( AVAL1 / SHIFT=&SJ ADJUSTOBS=(TRT01PN ='1') );
  MNAR ADJUST( AVAL2 / SHIFT=&SJ ADJUSTOBS=(TRT01PN ='1') );
  MNAR ADJUST( AVAL3 / SHIFT=&SJ ADJUSTOBS=(TRT01PN ='1') );
  RUN;
  PROC SORT DATA =OUTM1; BY _IMPUTATION_ TRT01PN USUBJID BASE; RUN;
/*Generate transpose of OUTM2 - skinny format before Step 3*/

/*Step 3: Run MMRM Analysis on Imputed Data */

PROC MIXED DATA=OUTM2 METHOD=REML;
  BY _IMPUTATION_;
  CLASS TRT01PN USUBJID AVISITN COUNTRY SEX;
  MODEL LCHG = TRT01PN AVISITN COUNTRY SEX TRT01PN*AVISITN LBASE /
  DDFM=KR; /*CHG AND BASE ARE BASED ON THE LOG-TRANSFORMED COUGH
FREQUENCY*/
  REPEATED / SUBJECT=USUBJID (TRT01PN) TYPE=UN;
  LSMEANS TRT01PN*AVISITN / CL DIFF PDIFF;
  ESTIMATE 'TRT S - P ON DAY 28' TRT01PN -1 1
           TRT01PN*AVISITN -1 0 0 1 / CL LOWER LOWERTAILED;
  ESTIMATE 'TRT S - P ON DAY 56' TRT01PN -1 1
           TRT01PN*AVISITN 0 -1 0 0 1 / CL LOWER LOWERTAILED;
  ESTIMATE 'TRT S - P ON DAY 84' TRT01PN -1 1
           TRT01PN*AVISITN 0 0 -1 0 0 1 / CL LOWER LOWERTAILED;
  ODS OUTPUT PARAMETERESTIMATES=PESTIMATES;
  RUN;
/*First, sort the data of estimates by visit (variable "LABEL") */
PROC SORT DATA=PESTIMATES; BY LABEL; RUN;

/*Step 4: Combining estimates from each imputed data set */
PROC MIANALYZE DATA=PESTIMATES;
  MODELEFFECTS ESTIMATE;
  STDERR STDERR;
  BY LABEL;
  ODS OUTPUT PARAMETERESTIMATES=MIPARM;
```

```
RUN;

DATA MIPARM;
  SET MIPARM;
  SHIFT= &SJ;
RUN;

/*----- Output multiple imputation results -----*/
DATA &OUTPARMS;
  SET &OUTPARMS MIPARM;
RUN;

%END;
%MEND MIPARMS;

/*Assume that the tipping point for the shift parameter that reverses the
study conclusion is between 0 and 100. The following statement performs

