multiple imputation analysis for each of the shift parameters 0,10,20,30,...,
100.*/

ODS LISTING CLOSE;
%MIPARMS (DATA=XXXX, SMIN=0, SMAX=100, SINC=10, OUTPARMS=PARMS1);

/* Step 5: Finding Tipping Point for Shift Parameter between 0 and 100 such
that p-value is less than 0.05, below is an example for a tipping point for
the shift parameter between 40 and 50.

For a two-sided Type I error level of 0.05, the tipping point for the shift
parameter is greater than 40. The following statement performs multiple
imputation analysis for shift parameters 40, 41, ..., 50*/

%MIPARMS (DATA=XXXX, SMIN=40, SMAX=50, SINC=1, OUTPARMS=PARM2);

/*The following statements display the p-values that are associated with the
shift parameters.*/

PROC PRINT LABEL DATA=PARM2;
  VAR SHIFT PROBT;
  TITLE 'P-VALUES FOR SHIFT PARAMETERS';
  LABEL PROBT='PR > |T|';
  FORMAT PROBT 8.4;
RUN;
```

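### The tipping-point code judges significance at two-sided 0.05 while the primary result is declared at one-sided 0.05, so a primary success with one-sided p between 0.025 and 0.05 would read as tipped at about zero shift

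*SAP*

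**What the plan says.** **Primary decision rule.** SAP 8.7 states that "the difference will be declared statistically significant if the one-sided p value is less than 0.05", and Protocol 8.9.4 has the same rule. SAP 9.6.1 adds: "One-sided p-values at 0.05 significance level will be used". The sample size in SAP 8.2 also rests on a one-sided 0.05 test.

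**Tipping criterion in the body text.** SAP 9.6.5 says: "The tipping point can be identified while the result is no longer statistically significant". It names neither a level nor a side.

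**Tipping criterion in the code.** Appendix A first scans a coarse grid of shifts starting at zero, "MIPARMS (DATA=XXXX, SMIN=0, SMAX=100, SINC=10, OUTPARMS=PARMS1", and then refines it. The Step 5 comment that explains how to read the result begins "For a two-sided Type I error level of 0.05, the tipping point for the shift" and goes on to an example range of 40 to 50. The column printed for each shift is the pooled p-value, with a label that opens "LABEL PROBT='PR > |T", that is, the two-sided p.

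**What happens between model and printout.** The model contrasts in the tipping-point block are one-sided, for example "TRT01PN*AVISITN 0 0 -1 0 0 1 / CL LOWER LOWERTAILED". Only the estimate and its standard error go on to PROC MIANALYZE, and no one-sided p-value is requested after pooling.

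**The concern.** A tipping-point analysis asks how far the missing-data assumption must be bent before the trial's conclusion changes. It can answer that only if it uses the criterion by which the conclusion was reached. Here the conclusion is reached at one-sided 0.05 and the code looks for its loss at two-sided 0.05, which is twice as strict in the favourable direction.

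Two consequences follow. First, a declared success with one-sided p between 0.025 and 0.05 has a two-sided p between 0.05 and 0.10, so the table would show it as non-significant at the first grid point, before any departure from missing at random. Second, if the shift is applied to serlopitant as 9.6.5 intends, a clearer success crosses the stricter threshold at a smaller shift than the one that overturns the actual conclusion. SAP 9.6.5 asks for clinical judgment on whether the tipping point is plausible, so a tipping point that belongs to a different criterion misinforms that judgment.

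**Working it through.** **Inputs.** From SAP 8.2: ratio 0.75, CV 0.64, 85 per arm, 15% dropout, 90% power, one-sided 0.05. Assumed here: a second true ratio of 0.82, to show a smaller effect.

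**Step 1: reproduce the plan's figure.**
- Log SD = √ln(1 + 0.64²) = 0.586. Log difference = |ln 0.75| = 0.2877.
- n per arm = 2 × (1.645 + 1.282)² × 0.586² / 0.2877² ≈ 71.1, so 72. The noncentral t also gives 72, with power 90.1%.
- Dropout: 72 / 0.85 = 84.7, so 85 per arm and 170 in total, as stated.
- A two-sided 0.05 test would need 88 (normal) or 89 (t) per arm, which becomes 104 or 105 after dropout, or 208 to 210 in total. The design is therefore one-sided 0.05.

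**Step 2: the two cut-offs at zero shift.** SE = 0.586 × √(2/n), df = 2n − 2, and the cut-off ratio is exp(−t × SE).

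| Evaluable per arm | SE | One-sided 0.05 (primary rule) | Two-sided 0.05 (Step 5) |
|---|---|---|---|
| 72 | 0.0977 | t = 1.656, ratio 0.851 | t = 1.977, ratio 0.824 |
| 85 | 0.0899 | t = 1.654, ratio 0.862 | t = 1.974, ratio 0.837 |

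An observed ratio between the two cut-offs is a success under SAP 8.7 and already tipped under Step 5.

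**Step 3: how often that happens.** Noncentral t with noncentrality |ln ratio| / SE. The zone is P(one-sided p < 0.05) minus P(one-sided p < 0.025).

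| Evaluable per arm | True ratio | p < 0.05 | p < 0.025 | Zone, all trials | Zone, share of successes |
|---|---|---|---|---|---|
| 72 | 0.75 | 90.1% | 83.3% | 6.8% | 7.5% |
| 72 | 0.82 (assumed) | 64.7% | 52.3% | 12.4% | 19% |
| 85 | 0.75 | 93.9% | 88.9% | 4.9% | 5.3% |
| 85 | 0.82 (assumed) | 71.0% | 59.3% | 11.7% | 17% |

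**Step 4: limits of the calculation.** It uses the design's two-sample t-test in place of the MMRM. Shift zero is a multiple-imputation analysis under missing at random, so its p-value will be close to the MMRM p-value but not identical. The statement about the zone is exact for the thresholds and approximate for a given dataset.

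**The case against.** The strongest reply is that the body of the SAP already settles the matter. Section 9.6.1 requires one-sided p-values at 0.05, section 9.6.5 speaks of loss of significance, and together they imply one-sided 0.05. The two-sided level sits in a comment and a print label in code offered as a sample, with a placeholder dataset name and a hypothetical range. No line of code applies a cut-off, so an analyst could read the one-sided answer from the same printout at 0.10. Part of this stands: the body text does point to the right rule, and nothing shows that the code would be run unchanged. It does not remove the conflict, because Step 5 is the only place that gives the tipping point a level, and it gives one the rest of the plan does not use. Elsewhere the same appendix follows the one-sided plan, with one-tailed contrasts and alpha = 0.1 for the responder intervals.

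The second reply is that the error is conservative: it can only make a positive result look less robust. This is correct, and it limits the weight of the point.

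A reader might infer three stronger things that the documents do not support:

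- **That the lost margin can be given in log units.** SAP 9.6.5 completes imputation before log transformation, and the code shifts untransformed cough rates. A log-scale shift is not one the plan applies, and converting it would need a cough-rate distribution that the documents do not give.
- **That the code as written understates the margin of every positive result.** That holds only if serlopitant's imputed values are shifted, as 9.6.5 intends. The code shifts TRT01PN = '1', which the same appendix defines as placebo. This is a separate defect; the zero-shift consequence does not depend on it.
- **That the copy-reference analysis contradicts the plan in the same way.** Its block pools by the same route and prints no one-sided p, but it states no two-sided level, and a one-sided p follows from the pooled estimate and standard error.

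**Conclusion.** The inconsistency is real and should be corrected before database lock. Read as written, Step 5 tests the robustness of the primary conclusion at one-sided 0.025, although that conclusion is drawn at one-sided 0.05. A success in the gap would be presented as fragile at about zero shift. Under the design assumptions this affects roughly 5% to 7% of trials at a true ratio of 0.75, and about 12% at an assumed 0.82, for 85 to 72 evaluable subjects per arm. For clearer successes the tipping shift would also be understated, provided the shift is applied to serlopitant; that amount is left unquantified.

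The effect is confined to how the sensitivity analysis is read. The primary decision and its type I error are untouched. The figures rest on the planning CV of 0.64, on normality on the log scale, and on the two-sample t-test as a stand-in for the MMRM.

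**What to change.** 1. In SAP 9.6.5, state that the tipping point is the smallest shift at which the pooled one-sided lower-tailed p-value for serlopitant minus placebo at Day 84 is no longer below 0.05.
2. In Appendix A, derive that p-value after pooling: PROBT/2 if the pooled estimate is below 0, otherwise 1 − PROBT/2. Reading the two-sided p against 0.10 with the estimate in the favourable direction is equivalent.
3. Replace the two-sided wording in Step 5, and print and label the one-sided p for each shift.
4. For consistency, report the same pooled one-sided p in the copy-reference analysis.

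The cost is a wording change and one line of derivation code. Data collection, sample size and the primary analysis are unaffected. The arm coding in the shift statements should be reconciled in the same revision, as a separate correction.

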## APPENDIX B: SCHEDULE OF ASSESSMENTS

## MTI-110 Schedule of Visit Activities

Study Procedures	Screening	Baseline	Treatment Period						Follow-up		
	Day -14 to Day -1 a,b	Day 0	Day 1 h	Day 14 k,o	Day 28 k	Day 56 k	Day 84 h,k	Day 85/ETD	Day 112 h,k,r	Day 113	
Written Informed Consent n	X										
Inclusion/Exclusion Criteria	X	X									
Demographics; Medical & Medication History	X	X d									
Chest Radiograph or CT Thorax l	X										
Physical Examination	X							X		X	
Vital Signs	X	X	X		X	X	X	X		X	
Height & Weight	X				X m	X m		X m			
ECG (12-lead)	X				X	X		X		X	
Spirometry	X										
Clinical Laboratory Sampling	X				X p	X p		X		X	
Urinalysis	X				X	X		X		X	
Urine Drug Screen	X				X	X		X		X	
Serum Pregnancy Test	X										
Urine Pregnancy Test		X			X	X		X		X	
PK Sample					X	X					
Attach Cough Monitor		X g			X g	X g	X f,g		X f,g		
Collect Cough Monitor			X f		X j	X j		X		X	
Adverse Event Monitoring			X	X	X	X	X	X	X	X	
Concomitant Medications	X	X	X	X	X	X	X	X	X	X	
LCQ		X			X	X		X		X	
Dosing Diary			Daily during treatment period								
Cough Severity VAS	X	X			X	X	X	X	X	X	
Study Drug Distribution and/or Accountability		X e	X e,i		X	X	X	X q			
Review Dosing Diary Entries			X	X	X	X	X	X			
PGIC					X	X		X			
CGIC								X			

Abbreviations: CGIC – Clinician’s Global Impression of Change; ECG – electrocardiogram; ETD – early treatment discontinuation; LCQ – Leicester Cough Questionnaire; PGIC – Patient’s Global Impression of Change; VAS – visual analog scale.

- a Multiple clinic visits may be required to complete all screening assessments.
- b The Screening Period may be fewer than 14 days. Additionally, the Screening Period may be extended beyond 14 days if the Menlo Therapeutics Medical Monitor requires additional follow-up on findings from any of the Screening assessments.
- c First dose of study drug administered on Study Day 1 after the cough monitor is removed and before 10am.
- d Medical and medication history only.
- e Study drug is dispensed in a lockbox if subjects do not return to the clinic for Day 1.
- f May be managed by mobile research nurses.
- g Cough monitor should be attached before 10am and worn for 24 hours during each assessment.
- h Visits may be conducted at subject's home (by mobile research nurses).
- i Mobile research nurses will retrieve the study drug from a lockbox on Day 1.
- j Cough monitor will be collected by a courier and delivered to the clinic on the following day.
- k Visit window is  $\pm$  3 days.
- l If not done within the past 5 years (considered to be part of standard of care in the UK).
- m Weight only
- n Informed consent must occur prior to any protocol-mandated procedures, including stopping of any excluded therapies. This may occur prior to Day -14.
- o Telephone visit.
- p Endocrine and reproductive endocrine tests are not done at Days 28 and 56.
- q ETD visit only at Day 85.
- r Day 112 not required if subject has discontinued treatment early.

## APPENDIX C: STUDY VISIT MAP WITH MATCHED INTERVAL ID

## Study Visits and Matched Interval IDs in Datasets

Study Procedures	Screening	Baseline	Treatment Period						Follow-up	
	Screening	Day 0 Study Day -1	Day 1	Day 14	Day 28	Day 56	Day 84	Day 85 /ETD	Day 112	Day 113
VISITNUM	1	2	3	4	5	6	7	8	9	10
Interval ID	148	149	150	151	155	156	157	158	159	160
Study Visit Window			1 ST DAY DOSING	± 3	± 3	± 3	± 3	± 3	± 3	± 3
Vital Sign Data a	X	X	X		X	X	X	X		X
Cough Severity VAS Monitoring Data a	X	X			X	X	X	X	X	X
Telephone Contact Data a				X						
Cough Monitoring Data b		X			X	X	X		X	

a Data collected at visits marked as X. Visit dates will be derived based on the following three datasets: vital sign, cough severity VAS monitoring, and telephone contact. If there is any discrepancy in a visit date, the date recorded in vital sign dataset will be considered as the primary date.

b The cough monitoring data has regular visits labeled as Baseline, Day28, Day56, Day84, and Day112, and the repeated visits labeled as Baseline-R, Day28-R, Day56-R, Day84-R and Day112-R. Both regular and repeated records at the specific visit will be included in analysis data. Repeated evaluations are usually due to equipment failures or unacceptable initial evaluations.

**Urine Microscopic**

7BAC	BACTERIA(/HPF)
V7OXC	CA OXALASTE CRYSTALS (/HPF)
7EPIR	EPITHELIAL RENAL (/HPF)
7EPIS	EPITHELIAL SQUAMOUS (/HPF)
7EPIT	EPITHELIAL TRANSITIONAL (/HPF)
V7GRC	GRANULAR CAST (/LPF)
7UHC2	HYALINE CAST (/LPF)
V7RCS	RBC CAST (/LPF)
7URBC	RBCS (/HPF)
V7TPC	TRI PHOSPHATE CRYSTALS (/HPF)
V7UAC	URIC ACID CRYSTALS
V7WAC	WAXY CAST (/LPF)
V7WCS	WBC CAST (/LPF)
7UWBC	WBCS (/HPF)
V7YST	YEAST (/HPF)

**Urine Drug Screen**

OPIATE	OPIATES
OXYCDN	OXYCODONE
HYDCDN	HYDROCODONE
HYDMRPHN	HYDROMORPHONE
OXMCC	OXYMORPHONE
MORPHINE	MORPHINE
CODEINE	CODEINE

**Pregnancy, Qualitative**

HCG	Choriogonadotropin Beta (ng/mL)
-----	---------------------------------

**Urine Pregnancy (reported on eCRF)****Other Tests (Manual Diff W/CALC ABS)****PK (Primary and Secondary)**
